### **Describe potential benefits and importance to the participants and others**

There are no direct benefits to participating. Information obtained as part of this study will serve as pilot data for federal grant applications launching a more comprehensive expansion of the intervention study regionally and through our international collaborations. Moreover, this work will inform the feasibility and scalability of a novel intervention aimed at (1) the promotion of resiliency and child development in children growing up in high-risk environments, (2) the prevention of child maltreatment and early adversity exposure, and (3) the reduction of lifetime disease and health consequences linked to adversity.

### **Discuss why risks are reasonable in relation to benefit**

The risks in this protocol are minimal to participants. Families are connected to SafeCare programs designed to improve child and family outcomes. The benefits of this study aid in the improvement of services for families exposed to adversity.

## **I. Statistical Methods**

### **Data Analysis**

**Analyses.** Analyses will be guided by Drs. [name] (Quantitative Psychologist) and [name] (Biostatistician).

For **Hypothesis 1a** we will analyze the satisfaction and usability responses gathered at the post-intervention, follow-up assessment using descriptive and inferential statistics. Descriptively, we will report central tendency (means, medians) and dispersion (standard deviation, interquartile range) measures for response distributions. To evaluate the significance of app appeal, we will conduct one sample Wilcoxon signed rank tests to determine if the central location of the data departs from point values that reflect slight or minimal satisfaction/usability.

Additionally, analysis of the qualitative focus group transcription will be completed using NVivo software. Broad themes within the transcription will be identified using a template approach. [name] (qualitative contractor) will code a sample and develop a specific codebook. Reliability will be established between [name] and one of her graduate students. Themes identified from the focus group will be used to update and finalize the mHealth app for future grants and studies.

**Hypothesis 1b** will involve mixed effects model analyses where positive parenting outcomes are regressed on a Tips indicator (tips delivered vs tips not delivered), a period indicator, and a random intercept term. The period indicator will assess outcome variability associated with the first two weeks vs the last two weeks of app engagement. An interaction term between the Tips factor and period factor will also be examined to determine if the intervention effect differs by order of presentation. We expect that parents will evidence greater engagement in positive parenting practices on days when they receive the mobile-based parenting tips and strategies relative to on days when they do not receive this content. Assuming no Tips by period interaction, the focal effect for testing this hypothesis will be the main effect of Tips Delivered.

**Hypothesis 1c** will be tested using a mixed effects model analysis where parenting subscale scores at baseline and post-intervention are regressed on an assessment time indicator, a randomization condition indicator, and a random intercept term. Assuming no interaction between assessment time and randomization group, the focal effect is the main effect of assessment time, which represents the pre-to-post difference in parenting scores.

**Hypothesis 2a** will be analyzed in the same manner as Hypothesis 1b replacing the parenting outcomes with child challenging and positive behavior counts. The hypothesis of behavioral improvement during weeks where parents receive tips will be tested by focusing on the main effect of the Tips indicator.

Finally, **Hypothesis 2b** will be analyzed in the same fashion on Hypothesis 1c. We hypothesized the child development scores will increase at the post-intervention assessment and this will be evaluated by testing the main effect of assessment timing.

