**A. Specific Aims**

This is an intervention study to provide in-the-moment parenting tips with the goal of educating parents about monitoring and promoting child development, thereby increasing healthy parent-child interactions leading to resiliency in high-risk children. Specifically, in a sample of parents participating in a HV program, we will use a smartphone app (mHealth app) to deliver twice-daily tailored messages with tips on monitoring and promoting child development. Ecological momentary assessments (EMA) of parents' emotions, parenting behaviors, and interactions with their children will also be collected via the mHealth app. Building off our previous work we expect that parents will evidence greater engagement in positive parenting practices on days when they receive the mobile-based parenting tips and strategies relative to on days when they do not receive this content.

We hypothesize that in-the-moment parenting tips delivered around peak times of parent-child interactions (i.e., before work/school, mealtimes, and bedtime) will promote positive parenting practices in a sample of parents at increased risk of adversity exposure. We aim to use EMA methodology to measure both group level differences (i.e., intervention vs. services as usual) and within-person fluctuations in harsh parenting, children's emotional and behavioral functioning, and positive parenting practices. The study will evaluate the following aims and hypotheses:

**Aim 1. Conduct a 2-arm, randomized, controlled crossover trial to examine the feasibility and effectiveness of a mobile-based parenting app with parents participating in HV services.**

Hypothesis 1a. Parents will report high rates of satisfaction and usability. Hypothesis 1b. Parents will evidence greater engagement in positive parenting practices on days when they receive the mobile-based parenting tips and strategies relative to days when they do not receive this content.

Hypothesis 1c. Groups will evidence increases in positive parenting subscale scores after a month of app engagement.

**Aim 2. Utilize EMA data and follow-up assessments to examine the impact of positive parenting practices on the promotion of child development.**

Hypothesis 2a. Hypothesis 2a. Children will demonstrate less challenging and more positive behavioral functioning on days when their parents receive positive parenting tips.

Hypothesis 2b. Groups will evidence increases in developmental scores after a month of app engagement.

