## Power Analysis

Hypothesis 1a is largely descriptive in nature, but all other hypotheses involve inferential tests of a within-group (repeated measures) effect. To evaluate statistical power, we calculated necessary sample sizes for a paired t-test. Analyses considered both a medium (0.35) and large (0.55) Becker g pre-post standardized mean difference ( $[M_{post} - M_{pre}]/SD_{pre}$ ) under two pre-post correlation conditions. With a Type I and II error set at 0.05 and 0.20, we estimated necessary sample sizes of 79 and 34 for medium and large

effect detection with the pre-post correlation equal 0.40. If the pre-post correlation was somewhat higher, at 0.60, necessary sample sizes drop to 54 and 23. Results suggest the study is powered to detect a moderate to large effect provided the pre-post correlation is of moderate strength.

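### Hypotheses 1b and 2a: the unit of analysis is not stated, and on day- or report-level rows a random intercept alone can make the Tips standard error too small

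*Combined protocol and SAP*

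**What the plan says.** Under I. Statistical Methods, Data Analysis, the Hypothesis 1b outcomes are "regressed on a Tips indicator (tips delivered vs tips not delivered), a period indicator, and a random intercept term". Hypothesis 2a "will be analyzed in the same manner as Hypothesis 1b replacing the parenting outcomes with child challenging and positive behavior counts". For neither does the plan name the row level, a random Tips slope, a person-by-period effect, a residual correlation structure, robust standard errors or a degrees-of-freedom method.

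The wording points both ways on the row level:

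- **Days or reports.** Hypothesis 1b expects "greater engagement in positive parenting practices on days when they receive the mobile-based parenting tips and strategies". Hypothesis 2a in A. Specific Aims expects "more positive behavioral functioning on days when their parents receive positive parenting tips". The same section aims to measure "within-person fluctuations in harsh parenting".
- **One value per period.** The test of Hypothesis 2a is described as one of "behavioral improvement during weeks where parents receive tips". The Power Analysis says that, apart from Hypothesis 1a, "all other hypotheses involve inferential tests of a within-group (repeated measures) effect", and for these "we calculated necessary sample sizes for a paired t-test".

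Under D. Research Design and Methods, each parent has one two-week block with tips and one without, in randomized order. Tips therefore changes once per parent.

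**The concern.** The information about Tips lies in one difference per parent: the tips fortnight against the other fortnight. More surveys within a fortnight measure each fortnight's level more precisely. They do not average out whatever else made that fortnight better or worse for that family.

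A random intercept removes stable differences between parents and nothing more. Fitted to day or report rows, the model divides all remaining variation by the number of reports, including variation shared by a whole fortnight or carried from one day to the next. The Tips standard error is then too small.

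Two analysts could follow this text faithfully, one using daily rows and one using period means, and report different p-values. H. Risks and Benefits says the results will serve as pilot data for federal grant applications, so intervals that are too narrow would carry into later planning.

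**Working it through.** **1. The plan's own figures.** For a two-sided paired t-test with equal SDs, d = g / √(2(1 − r)), α = 0.05 and power 0.80. The plan does not state sidedness; two-sided reproduces its figures.

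| g | r | d | n computed | n in plan |
|---|---|---|---|---|
| 0.35 | 0.40 | 0.35/√1.2 = 0.320 | 79 | 79 |
| 0.55 | 0.40 | 0.55/√1.2 = 0.502 | 34 | 34 |
| 0.35 | 0.60 | 0.35/√0.8 = 0.391 | 54 | 54 |
| 0.55 | 0.60 | 0.55/√0.8 = 0.615 | 23 | 23 |

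All four reproduce, so the power basis is one difference per parent. A row-level random-intercept analysis would not match it.

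**2. Inputs for the error rate.** From the documents: up to 50 parents, two 14-day periods, and one survey a day (E. Procedures) or two (Study Design; Data Sources), so m = 14 or 28 reports per period. Assumed, because the documents give no values: 25 parents per order, no Tips effect, complete reports, total variance 1, between-parent share 0.4, person-by-period share τ² from 0 to 0.10, and residual σ² = 0.6 − τ².

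**3. Formulas.** True variance of one parent's difference: V = 2τ² + 2σ²/m. The random-intercept model uses about M = 2s²/m, with s² = [σ²(2m − 2) + σ² + mτ²]/(2m − 1). The true SE divided by the model SE is R = √(V/M), and the type I error is about 2[1 − Φ(1.96/R)].

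**4. Example, m = 14 and τ² = 0.02.** V = 0.04 + 2(0.58)/14 = 0.1229. s² = (0.58×26 + 0.58 + 0.28)/27 = 0.5904, so M = 0.0843. R = √(0.1229/0.0843) = 1.21, and the type I error is about 10%.

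**5. Results.**

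| Person-by-period share of total variance | R, m = 14 | Type I error, m = 14 | R, m = 28 | Type I error, m = 28 |
|---|---|---|---|---|
| 0 | 1.00 | 5% | 1.00 | 5% |
| 1% | 1.11 | 8% | 1.21 | 10% |
| 2% | 1.21 | 10% | 1.39 | 16% |
| 5% | 1.47 | 18% | 1.84 | 29% |
| 10% | 1.86 | 29% | 2.45 | 42% |

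Simulation of balanced crossovers agrees within about a point or two.

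**6. Other departures (simulated, same base assumptions).**

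- Positive serial correlation alone, AR(1) of 0.1, 0.2 and 0.3: about 7–8%, 10–11% and 13–15%.
- Negative serial correlation of −0.1 and −0.2: about 3% and 2%, so the test becomes conservative.
- An unmodelled morning/evening difference of 0.5 or 1.0 SD with 28 reports: 4% and 2%. With a 2% person-by-period share as well, the error falls from 16% to 14% and 10%.
- Individual tip effects with SD 0.1 to 0.3: the 95% interval for the average effect misses it 6–17% of the time (14 reports) or 7–25% (28). This concerns coverage of the average effect, or an effect that averages zero. It does not arise if tips affect no one.
- 60% completion varying by parent, shares of 1 to 10%: 7–22% (14 scheduled) and 8–35% (28 scheduled).
- Counts for Hypothesis 2a, under an assumed random-intercept Poisson model with 0.5 to 2 events per report and fortnight log-SD 0.1 to 0.3: 7–32% (14) and 8–48% (28). At 0.1 events per report: only 5–7% and 6–9%.

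**7. The alternatives.** The crossover test on period means held 4–6% throughout. A normal model with parent, person-by-period and AR(1) terms, tested on 48 df, gave 3.2–5.0% in seven settings where the random-intercept model gave 1.8–30.9%. A count model with the added person-by-period effect gave 4.0–5.3%.

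**The case against.** The strongest reply is that this is an ambiguity with a valid reading. The reference to weeks under Hypothesis 2a and the paired t-test power basis both fit period means, and on period means the stated model is sound. Harm needs two further things: rows fitted at day or report level, and extra correlation within a parent beyond the mean. That stands, and it is why the point is conditional. It does not dispose of the point, because both hypotheses are worded in days and nothing in the plan tells the analyst to average.

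A second reply is that the documents barely support person-by-period variation. They say home-visiting services continue during the study and that families differ in visits and curriculum stage. Stable differences of that kind go into the random intercept, and change between fortnights is an inference. This is fair. The documents make such variation plausible and say nothing about its size.

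Third, the plan names no distribution for the counts, so the Poisson figures do not describe a planned analysis. This also stands; they show direction only.

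Finally, the 4–6% for period means is for the unconditional test. The plan makes the Tips main effect focal only if there is no Tips-by-period interaction. That conditional step and carryover were not simulated, and the change proposed here does not address them.

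**Conclusion.** The concern holds as a conditional one. The unit of analysis for Hypotheses 1b and 2a is not stated. On the day- or report-level reading, the specified model can understate the Tips standard error because Tips varies only between two blocks within each parent.

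Under the assumed variances, a person-by-period share as small as 2% doubles the nominal 5% error with 14 reports per period and triples it with 28. With no departure there is no inflation, and with negative serial correlation or a morning/evening difference alone the error runs the other way. The actual size in this trial cannot be known from the documents. The plan should be corrected, since one natural reading gives unreliable intervals for two hypotheses and the remedy is cheap. Confidence is medium.

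**What to change.** State the unit of analysis for Hypotheses 1b and 2a, then take one of two routes.

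- **Day or report rows:** add a person-by-period random effect (or a random Tips slope) and a within-person serial-correlation term. Test Tips on parent-level degrees of freedom, the number of parents minus 2 (48 with 50 parents).
- **Period means:** compare each parent's two period means with the standard 2x2 crossover test. This also matches the power basis and is the fallback if the fuller model does not converge.

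For Hypothesis 2a, use each parent's mean count per completed report in the crossover test, which remains defined when a count is zero. Alternatively, name a count model with the same added random effect.

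Separately, reconcile the once-daily survey schedule in E. Procedures with the twice-daily schedule in Study Design and Data Sources. The conflict changes the number of reports, not whether the model is valid.

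The cost is two or three sentences and no new data. With no departure, the period-mean interval is about 2–3% wider (t quantiles 2.011/1.962 = 1.025). With person-by-period shares of 1 to 10% it is about 1.13 to 1.90 times as wide (14 reports) or 1.23 to 2.50 times (28). That extra width is uncertainty the random-intercept model leaves out.

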#### **D. Research Design and Methods (What, When, How, Where)**

##### **Study Design**

We will use a 2-arm randomized, controlled cross over trial design to evaluate the effectiveness of the mHealth Intervention. We will recruit up to 50 participants from three home visiting programs (SafeCare at NorthCare, Latino Community Development Agency [LCDA], and Parent Child Center [PCCT]). All three of these programs utilize the SafeCare home visiting model, which includes modules on healthy parent-child interactions and promoting parenting skills in high-risk families. We plan to recruit existing and new families in these programs and randomly assign them to receive either 2 weeks of the mHealth intervention + EMA data collection followed by 2 weeks of only EMA data collection or to receive 2 weeks of only EMA data collection followed by 2 weeks of mHealth intervention + EMA data collection. All participants will receive both conditions in counterbalanced order.

Study participation involves consenting to administrative record release and immediate baseline questionnaires assessing demographics, the child's exposure to adversity, parental exposure to childhood adversity, parent's emotional expression, emotion reactivity, and emotion regulation and the child's emotion regulation and development, ecological momentary assessment (EMA) at fixed times twice a day (morning and evenings), and final assessments, which will be the same as the baseline assessments.

**EMA Only Condition** In the EMA only condition, families will continue to receive services utilizing the SafeCare home visiting model, including modules on healthy parent-child interaction and promoting parenting skills in high-risk families, but they will not receive parenting tips via the mHealth app during this period. We plan to administer brief surveys via the mHealth app twice a day at pre-determined times (morning and evening). These surveys will ask parents to provide information about where they are and

with whom, their emotional state, recent parent-child interactions, current stressors or challenges, and their child's emotional and behavioral functioning. Parents will receive these twice daily surveys every day for two weeks.

[figure not shown]

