### **mHealth Intervention Condition**

When families are in the mHealth intervention condition, the mHealth app will deliver parenting tips and strategies twice daily for 14 days. Furthermore, we plan to administer brief surveys via the mHealth app twice a day at pre-determined times (morning and evening). These surveys will ask parents to provide information about where they are and with whom, their emotional state, any recent parent-child interactions, and any current stressors or challenges. Parents will receive these twice-daily surveys and the parenting tips for every day for two weeks.

Of note, during the 4-week EMA study, parents will receive either 2 weeks of the mHealth intervention + EMA data collection followed by 2 weeks of only EMA data collection or to receive 2 weeks of only EMA data collection followed by 2 weeks of mHealth intervention + EMA data collection.

The order of mHealth intervention and EMA data collection will be counterbalanced across participants to allow for a within-subjects comparison.

See the study diagram below for a visual depiction of our data collection schedule.

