### **App Feasibility and Effectiveness Data**

We will also collect data on parents' perceptions of app feasibility and effectiveness via survey and a focus group selected from a subset of the 50 participants (up to n =30). We will also track app use (e.g., assessment response rates, number of missing assessments, time spent on app, type of OnDemand content viewed) to provide insight into participant compliance and app interaction.

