### **Information security**

All survey data are collected using REDCap. REDCap is a secure web application for managing survey data. REDCap allows for live data capture, meaning data are immediately stored on secure University servers. REDCap data may only be accessed by study staff using University encrypted devices. Access to study survey data is provided only to data collectors (so they may keep in contact with survey participants) and to personnel who will use data for analysis and reporting.

All trial data related to the parenting intervention will be collected and monitored via the Insight mHealth Platform. The Insight™ Platform will enable the researcher team to create an innovative mobile application that: 1) identifies proximal and distal antecedents to imminent risk behaviors using self-report surveys (i.e., ecological momentary assessments [EMAs]); and 2) conduct a Just-in-Time Adaptive Intervention (JITAI) that

tailors intervention content in real-time based upon survey responses. Insight™ is utilizes a web-based content management system (CMS) for easy access across multiple browsers, and uses architecture that enables the incorporation of new features. Users of this service log into a web-based CMS and follow step-by-step guidance to create and manage research studies, enroll and monitor study participants, create EMA items, create different types of EMAs (e.g., random, daily, participant-initiated) and create specific assessment rules (e.g., two vs. four random assessments per day). Once study parameters and content have been created in the CMS, researchers transfer their study materials into the smartphone application shell. The customized smartphone application can be made available on the Android app store, and will soon be available on the Apple app store. Data are encrypted within the smartphone application and automatically and securely uploaded into mHealth servers. Encrypted data can be downloaded from the server by users at any time. The PIs will monitor the incoming data from the Insight™ platform on a monthly basis to ensure that the trial is conducted according to the approved protocol.

All paper forms are kept in locked filing cabinets behind a locked door in an office requiring a security badge for entry.

Consents will be collected electronically through REDCap and stored electronically on a secure OUHSC server.

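### H1b and H2a take no account of unanswered surveys: the response data are tracked but not linked to the Tips contrast, and answering that depends on condition together with time of day or the outcome could bias it

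*Combined protocol and SAP*

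**What the plan says.** **Models.** For Hypothesis 1b, positive parenting outcomes are "regressed on a Tips indicator (tips delivered vs tips not delivered), a period indicator, and a random intercept term". A Tips-by-period interaction is also examined and, if there is none, the Tips main effect is the focal test. Hypothesis 2a "will be analyzed in the same manner as Hypothesis 1b replacing the parenting outcomes with child challenging and positive behavior counts".

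**App load.** In the EMA-only fortnight, Study Design says "Parents will receive these twice daily surveys every day for two weeks" and, of the same parents, that "they will not receive parenting tips via the mHealth app during this period". In the other fortnight, the mHealth Intervention Condition section says "the mHealth app will deliver parenting tips and strategies twice daily for 14 days" and "Parents will receive these twice-daily surveys and the parenting tips for every day for two weeks". The Ecological Momentary Analysis (EMA) Data section also gives morning and evening surveys. Quantitative procedures disagrees: there the survey comes once daily, in the evening, alongside twice-daily tips.

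**Response data.** App Feasibility and Effectiveness Data says that the study will track "assessment response rates, number of missing assessments, time spent on app" and similar measures, to learn about compliance and use of the app. Administrative Data adds that family characteristics may be examined as predictors of app use. Neither section mentions the Tips contrast. Statistical Methods gives no missing-data method or assumption, no comparison of response by condition and no sensitivity analysis.

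**The concern.** An outcome exists only for a survey that was answered. The plan does not say how missed surveys are handled, but no imputation is planned, and a mixed model uses the records it has. The tips come through the same app that collects the outcome. They could remind parents to answer or tire them of answering, so the response pattern may follow the condition.

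The planned safeguards cover part of this. Randomized order and the period term deal with change over the four weeks, and the random intercept deals largely with stable differences between parents. None of them deals with a parent who skips the survey at hard moments, or in the mornings, more in one fortnight than in the other. Hypotheses 1b and 2a are the trial's only comparisons of tips with no tips, and the results are meant as pilot data for grant applications. A spurious shift in either direction would therefore carry forward.

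**Working it through.** **1. The plan's own figures.** For a paired t-test with dz = d/√(2(1 − r)), two-sided alpha 0.05 and power 0.80, the noncentral t distribution gives N = 79 and 34 (d = 0.35 and 0.55, r = 0.40) and 54 and 23 (r = 0.60). All four match the Power Analysis section and are not in dispute. They contain no allowance for unanswered surveys.

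**2. App contacts per fortnight**, counting each tip and each survey as one contact:
- Study Design and mHealth Intervention Condition: 14 × 2 = 28 without tips; 14 × (2 + 2) = 56 with tips.
- Quantitative procedures: 14 × 1 = 14 without tips; 14 × (1 + 2) = 42 with tips.

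The load is unequal on either reading, unless tips are delivered inside the survey.

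**3. Bias from outcome-dependent answering.** Let p1 and p0 be the response rates with and without tips, and let G be the mean of answered minus unanswered reports, taken as equal in both conditions. The overall mean is p × answered + (1 − p) × unanswered, so the answered mean exceeds the overall mean by (1 − p)G. Hence

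bias = (1 − p1)G − (1 − p0)G = G(p0 − p1).

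This is zero if G = 0 (answering unrelated to the outcome) or if p1 = p0. With assumed rates of 75% with tips and 65% without, G = 0.25 SD gives −0.025 SD and G = 0.5 SD gives −0.05 SD. Reversing the rates reverses the sign.

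**4. Bias from time of day** (twice-daily surveys only). Assume evenings are 80% answered in both conditions, and mornings 80% without tips but 50% with tips. Mornings then make up 0.50/(0.50 + 0.80) = 0.385 of the answered reports with tips, against 0.500 without. If morning reports are lower by D, bias = D × (0.500 − 0.385): 0.3 × 0.115 = 0.035 SD, or 0.5 × 0.115 = 0.058 SD. In simulations of these two settings, a morning/evening term brought the bias to zero.

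**5. Simulation of the planned model.** Random-intercept fit with Tips and period; no interaction term; variances treated as known; 50 parents; 28 prompts per fortnight; total SD 1; ICC 0.4 (assumed); true Tips effect 0; 400 runs. Here g is the log-odds of answering per within-person SD of the outcome.

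| Answered, tips / no tips | Answering depends on | Bias (SD) | Type I error |
|---|---|---|---|
| 60% / 80% | nothing else | 0.000 | 5.0% |
| 60% / 80% | parent's own mean only | +0.004 | 5.8% |
| 75% / 75% | outcome, g = 0.5 in both | 0.000 | 5.0% |
| 65% / 80% | outcome, g = 0.25 | +0.030 | 15% |
| 65% / 80% | outcome, g = 0.5 | +0.057 | 40% |
| 60% / 80% | outcome, g = 0.5 | +0.075 | 56% |
| 80% / 65% | outcome, g = 0.5 | −0.052 | 34% |
| 75% / 75% | outcome, g = 0.5 with tips, 0 without | +0.093 | 80% |

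The last row shows that equal response rates are not enough if selectivity differs by condition.

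**6. Scale.** With 50 parents, 80% power needs dz = 0.404. The detectable Tips effect is 0.404 × √(2(1 − ICC − v)/m + 2v), where m is reports per fortnight and v is the parent-by-fortnight share of variance (both assumed).
- ICC 0.5, m = 28, v = 0: 0.404 × √(1.0/28) = 0.076 SD.
- ICC 0.5, m = 28, v = 0.10: 0.404 × √(0.8/28 + 0.2) = 0.193 SD.
- ICC 0.3, m = 10, v = 0.10: 0.404 × √(1.2/10 + 0.2) = 0.229 SD.

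A bias of 0.03 to 0.08 SD thus ranges from about one eighth of the detectable effect (0.03/0.229) to about all of it (0.075/0.076).

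**The case against.** **What stands.** A gap in response rate does not by itself bias a likelihood-based mixed model, as the first two rows of the table show. The documents give no response rates, so no bias can be asserted, only the possibility of one. The smallest detectable effect, 0.076 SD, needs every survey answered and no parent-by-fortnight variance. With 10% such variance it is 0.19 to 0.23 SD, and the bias is then a fraction of it. This is a pilot of up to 50 parents, so the remedy should be light. Nothing in the plan forbids reporting response by condition; it simply does not provide for it.

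**Stronger readings that the documents do not support.**
- A reader might infer that answering must differ by design, because the platform "tailors intervention content in real-time based upon survey responses". That sentence is in Information security and describes what the platform enables. Tailoring the content of a tip does not in itself change the chance that a survey is answered.
- A reader might carry the formula to 0.15 SD (80% against 60%, G = 0.75 SD). In the simulation, even g = 1 at 60% against 80% gives 0.124 SD, so 0.15 SD needs more than e^1 = 2.7-fold odds of answering per within-person SD. That is an extreme case.
- A reader might ask for a weekend term. Each condition runs for 14 consecutive days and so contains two weekends; the term would add little.
- Morning skipping cannot be taken as given, because Quantitative procedures has evening surveys only. On that reading the mechanism in step 4 does not exist.

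**Conclusion.** The gap is real and can be corrected cheaply. The Hypothesis 1b and 2a models take no account of who answers and when, and the tracked response data are not connected to the Tips effect. Bias needs two things together: answering that depends on time of day or on the momentary outcome, and a response rate or selectivity that differs between the fortnights. Under assumed gaps of 15 to 20 points and moderate selectivity (g = 0.25 to 0.5), the bias is about 0.03 to 0.08 SD, upward if tips depress answering and downward if they raise it, supposing parents answer more readily at better moments.

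These sizes rest on assumed rates, ICC and selectivity. The error rates also rest on known variances and no parent-by-fortnight variance, so they are less portable than the bias figures. Hypothesis 2a concerns counts, to which an SD shift does not transfer directly. The results show direction and range; they do not predict what this trial will find.

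**What to change.** 1. Reconcile the survey frequency in Study Design, mHealth Intervention Condition and EMA Data (twice daily) with Quantitative procedures (once daily, evening). State whether tips arrive separately or inside the survey.
2. If surveys are twice daily, add a morning/evening term to the Hypothesis 1b and 2a models. If they are evening only, this step falls away.
3. Analyse answered/missed for each scheduled survey on Tips and period in the same crossover structure, with a binary-outcome model, and report it beside Hypotheses 1b and 2a.
4. State the missingness assumption of the main models. Add one delta-shift sensitivity analysis that shifts unanswered reports by condition and gives the shift at which the Tips conclusion changes. For Hypothesis 2a, use a scale suited to counts, such as a ratio of means.

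Step 2 deals only with skipping linked to time of day. Step 3 shows whether response rates differ, but it cannot show whether answering depends on unseen outcomes; step 4 covers that. The cost is some added programming and possibly a more cautious conclusion. The response data are already to be tracked through the app, so nothing more is asked of parents.
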